## **14.6 Assessment of Severity**

Severity of AEs will be classified following the U.S. National Institutes of Health Common Criteria for Adverse Events 5.0 (CTCAE), available Terminology online at https://ctep.cancer.gov/protocolDevelopment/electronic applications/docs/CTCAE v5 Quick R eference 8.5x11.pdf, published: November 27, 2017, with the exception of QTc prolongation, which will be graded as specified .in table 3. If the specific event is not contained in this compendium, the following generic definition, which is also contained in CTCAE 5.0 for such events, will apply:

- Grade 1: Mild; asymptomatic or mild symptoms; clinical or diagnostic observations only; intervention not indicated.
- Grade 2: Moderate; minimal, local or non-invasive intervention indicated; limiting ageappropriate instrumental activities of daily life (ADL)\*.
- Grade 3: Severe; significant but not immediately life-threatening; hospitalization or prolongation of hospitalization indicated; disabling; limiting self-care ADL\*\*.
- Grade 4: Life-threatening consequences; urgent intervention indicated.
- Grade 5: Death related to AE.

\*Instrumental ADL refer to preparing meals, shopping for groceries or clothes, using the telephone, work or farming, managing money, etc.

\*\*Self care ADL refer to bathing, dressing and undressing, feeding self, using the toilet, taking medications, and not bedridden.

Grade 1	Grade 2	Grade 3	Grade 4	Grade 5
(1) Absolute QTcF >480 and ≤500 ms and QTcF change from baseline >0 ms and ≤30 ms; or	(1) Absolute QTcF >480 ms and ≤500 ms and QTcF change from baseline >30 ms and ≤ 60 ms; or	1) Absolute QTcF >500 ms; or	Life-threatening consequence, e.g., torsades de pointes or other associated serious ventricular dysrhythmia.	-
(2) absolute OTcF	(2) absolute OTcF	(2) absolute OTcF		-
≤480 ms and QTcF	≤480 and QTcF	>480 and QTcF		
change from	change from	change from		
baseline >30 and ≤60	baseline >60 ms.	baseline >60 ms.		
ms				

#### Table 2: definition of severity grading of QTcF prolongation

This deviation from the CTCAE severity grading is necessary due to the specific situation of TB patients; a population in whom a change in QTc over baseline is difficult to assess. Before

treatment starts, they are sick, have elevated temperature and are distressed by their first contact with the trial team, which influences the QT interval, through elevated heart rate and possibly other mechanisms.

In a specific analysis of the Oflotub phase III study, it was confirmed that the elevated heart rates at baseline were associated with lower QTcF; and that specifically at baseline, QTcF correction undercorrects at these high heart rates of TB patients [76].

Further, QTc at baseline and late during treatment were compared. A mean increase in QTcF of 11.2 ms was found in the Gatifloxacin arm, and 9.8 ms in the control arm; despite the fact that for none of the drugs, a correlation between Cmax and QTc prolongation could be described.

Due to this limitation, there is a risk that an incorrect signal of QTcF prolongation over baseline in a patient will occur that in itself will not show a safety hazard to the patient, but will result in lifesaving drugs being withheld. Therefore, assessment of severity of QTcF prolongation and the stopping of treatment in this study as laid out in *Table 2: definition of severity grading of QTcF prolongation*, follows the precedent of the ACTG A5343 trial mentioned above; where a combination of bedaquiline and delamanid was trialled and assessed for its potential to prolong the QT interval [77].

Here, in order to prevent a false signal that might be due to a change in heart rate between assessments, a higher grade QTcF prolongation is defined as a combination of QTcF prolongation from baseline with an elevated absolute value, not a prolongation alone.

#### 14.7 Other AE definitions

The following definitions will be used for AE Reporting:

#### Action Taken with Study Drugs

- IMP unchanged
- IMP interrupted
- IMP stopped
- Non IMP study drug unchanged
- Non IMP study drugs interrupted
- Non IMP study drugs stopped
- Not applicable

#### **Other Action Taken**

- None
- Medication given
- Hospitalisation or prolongation of hospitalisation
- Therapeutic or diagnostic procedure

#### Outcome

- Resolved
- Improved

Protocol No: PanACEA - DECODE - 01/ LCB01-0371-20-2-02 Protocol Version No: V2.1, dated 08 September 2021

- Unchanged
- Worse
- Fatal
- Unknown

#### Occurrence

- Once
- Intermittent
- Continuous

## 14.8 Adverse event reporting

Adverse events will be recorded by the investigator from the time a participant signs the informed consent form.

Any AE (serious or non-serious) observed by the investigator or reported by the subject will be recorded in the source data and on the Adverse Event electronic case report form (eCRF). The Investigator will review each AE and assess its relationship to the study treatment based on all available information at the time of the visit. The following information will be recorded for each AE reported:

- Diagnosis of the AE, if possible. In the case where an overall diagnosis cannot be made, each specific sign and/or symptom will be recorded as individual AEs; where possible the wording in the CTCAE should be used.
- Date of onset
- Stop date (duration) if applicable
- Severity (grade)
- Action taken with IMP/non-IMP study drugs
- Other action taken
- Outcome
- Relationship to IMP/non-IMP study drugs
- Occurrence
- Seriousness

#### 14.9 Serious adverse event reporting

Any AE that occurs which is serious, or which is potentially serious, but a decision cannot be taken due to a lack of information, must be reported by the investigator to the study monitor and to the sponsor medical expert within 24 hours of the site first being aware of the SAE, whether or not the serious event is deemed drug-related. Medical Review will be done by the Sponsor Medical Expert. Furthermore, any SAE will be reported to Otsuka Novel Products GmbH, with its principal recipient in the United States, and secondary at [name], Germany.

In addition, the investigator will provide a detailed, signed, written, and complete SAE Form, including the investigator's estimates of the relationship with the study drug and seriousness of the AE in question to the study monitor and sponsor medical expert within 24 hours of becoming aware of the SAE. The investigator will ensure that the participant in the report is identified by an anonymous code rather than by personal details.

The study monitor will confirm receipt of the SAE Form with the Investigator and review the initial information on the SAE Form for diagnosis, consistency and completeness of data. To update or add information to a reported SAE, the Investigator will provide the study monitor and sponsor medical expert with a newly completed Serious Adverse Event Form, designated as a follow-up report. This will be submitted to the study monitor and Sponsor Medical Monitor within 24 hours of the Investigator receiving the information.

If additional information is needed to complete the profile of the reported SAE, the additional information will be requested from the Investigator, if necessary, to complete the profile of the SAE reported. After evaluation of the SAE Form for expectedness and possible relation to study drug, the sponsor/designee will complete a standardized form by the *Council for International Organizations of Medical Sciences* (CIOMS) for unexpected treatment-emergent SAEs (SUSARs), which are forwarded to the investigator. All SAEs and SUSARs will be submitted to all IECs/IRBs and regulatory bodies in accordance with local requirements and ICH-GCP guidelines.

## 14.10 Clinical Laboratory adverse events

Changes in the results of the clinical laboratory assessment, which the Investigator feels are clinically significant, will be reported as adverse events. It is the Investigators' responsibility to review the results of all laboratory tests as they become available. This review must be documented by the Investigators' dated signature on the laboratory report.

For each abnormal laboratory test result, the Investigator needs to ascertain if this is a clinically significant change from baseline for that individual patient. This determination, however, does not necessarily need to be made the first time an abnormal value is observed. The Investigator may repeat the laboratory test or request additional tests to verify the results of the original laboratory tests.

If this laboratory value is determined by the Investigator to be a negative, clinically significant change from baseline for that patient, it is an adverse event.

#### 14.11 Pregnancy as adverse event

All women of childbearing potential will be instructed to contact the investigator immediately if they suspect they might be pregnant during the trial (for example, missed or late menses). If pregnancy is suspected while the patient is receiving experimental study treatment, this will be withheld immediately until pregnancy can be ruled out with certainty.

If pregnancy is confirmed, experimental treatment will be permanently discontinued in an appropriate manner. The patient should complete her TB treatment course following the host country's national guidelines.

The investigator must immediately notify the sponsor of any pregnancy in a study subject. The pregnancy must be recorded on the pregnancy form and forwarded to the sponsor. Expedited reporting of pregnancy to regulatory authorities is necessary in case of a pregnancy complication fulfilling the criteria for Serious Adverse Events.

Protocol-required procedures for trial discontinuation must be performed unless contraindicated by the pregnancy. Other appropriate pregnancy follow-up procedures should be considered if indicated. In addition, the investigator must report to the sponsor for follow-up information regarding the course of the pregnancy, including perinatal and neonatal outcome. Infants must be followed for a minimum of 6 months. Congenital malformations are to be reported as Serious Adverse Events.

## 14.12 Disease under study

Symptoms of the disease under study (i.e. TB) experienced by the subject whilst on the study will be assessed by the Investigator. If the symptom has worsened whilst the subject is on the study, and the Investigator assesses it as clinically significant, it will be recorded as an adverse event.

If there is no change and the Investigator assesses the symptom as due to the subject's TB and not clinically significant, it will not be recorded as an AE, and this will be noted in the patient's source documentation. If the Investigator is unsure as to whether the symptom is clinically significant or not, it is to be classified as significant and reported as an AE.

If during follow-up phase, the participants is found to have at least one spot sputum sample that is found to be associated with relapse or re-infection with a different strain of MTB, this is to be recorded as adverse event.

## 14.13 Follow-up of adverse events

#### 14.13.1 General Follow-up of Adverse Events

During and following a patient's participation in a clinical trial, the Investigator must ensure that adequate medical care is provided to the patient for all AEs, including significant abnormal laboratory values. The investigator should inform the patient when medical care is needed for any AEs, he/she becomes aware of.

All non-serious AEs classified as severe and probably/possibly related to IMP must be followed until the AE has resolved, or until there is no further change likely to the participants' condition. Cases of pre-existing chronic conditions or if the patient dies from another event can be closed with an outcome of "unchanged".

All other non-serious AEs must be followed until the outcome of the event is "improved" (for chronic conditions), "resolved" or until the last scheduled study visit, and all queries on these AEs have been resolved. If the patient dies from another event, the case can be closed with an outcome of "unchanged".

All SAEs must be followed until the outcome of the event is deemed "resolved", "unchanged" or "fatal" and until all queries have been resolved. Cases of chronic conditions, cancer or if the patient dies from another event can be closed with an outcome of "unchanged".

#### 14.13.2 Follow-up of Post-Trial Adverse Events

Any new SAEs reported by the patient to the Investigator that occur after the last scheduled contact, that are determined by the Investigator to be causally related or possibly related to the use of the IMP, will be reported to the study monitor and sponsor medical Expert, IEC/IRB and regulatory authorities on an expedited basis as required.

# 15 STATISTICAL CONSIDERATIONS

## 15.1 Sample size determination

15 participants per arm with a total of 75 participants, and a wide range of DZD doses (from 0mg to 800mg BID) has been determined as an adequate sample size for population PK modelling, and for exposure response modelling to detect a clinically meaningful dose-dependent relationship.

Furthermore, the planned sample size of 15 subjects per treatment group is in keeping with other trials of this type and accounts for the possibility of up to 3 drop-outs per group, which based on previous studies of this type conducted at these sites, represents a conservative estimate of the expected drop-out rate.

Previous Phase IIA (EBA) studies indicate that the between patient standard deviation of logCFU can be approximately 0.2. Therefore, assuming similar variability in this trial the expected standard errors of group mean EBA and corresponding width of 95% confidence intervals are 0.052 and 0.101 respectively for a group size of 15 and 0.063 and 0.124 respectively for a group size of 10. This level of precision with a group size of 15 is considered adequate.

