#### 9.1.2 Primary Efficacy Endpoint

The efficacy of DZD will be evaluated by measuring the change in mycobacterial load over time on treatment as quantified by time to positivity in BD MGIT 960® liquid culture described by non-linear mixed-effects methodology

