4.3. Sample Size Determination

15 participants per arm with a total of 75 participants, and a wide range of DZD doses (from 0mg to 800mg BID) has been determined as an adequate sample size for population PK modelling, and for exposure response modelling to detect a clinically meaningful dose-dependent relationship.

Furthermore, the planned sample size of 15 participants per treatment group is in keeping with other trials of this type and accounts for the possibility of up to 3 drop-outs per group, which based on previous studies of this type conducted at these sites, represents a conservative estimate of the expected drop-out rate.

Previous Phase IIA (EBA) studies indicate that the between patient standard deviation of logCFU can be approximately 0.2. Therefore, assuming similar variability in this trial the expected standard errors of group mean EBA and corresponding width of 95% confidence intervals are 0.052 and 0.101 respectively for a group size of 15 and 0.063 and 0.124 respectively for a group size of 10.

This level of precision with a group size of 15 is considered adequate.

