To establish an exposure-response model for delpazolid, the change in liquid culture MGIT time to positivity (TTP) will be modeled and linked to derived PK metrics. Software and data management will be as described in section 8 (popPK model). The TTP data will be transferred from the responsible CRO (Tecro) in a consistent format. There are two TTP observations from each sampling point and those will be included separately as individual observations (no averaging). In the primary analysis, the MITT analysis population will be used. For patients discontinuing study medications prematurely (before 16 weeks), TTP data collected after the discontinuation will be excluded. Contaminated culture results will be ignored.

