12.2. Analysis of negative sputum culture on solid media

LJ solid media will be performed at the following visits only: WK00, WK08, WK12, WK16, and FU1-FU4. The proportion of participants with culture negative timepoint at each visit will be calculated by treatment arm for each of the ITT and AA analysis populations. Participants will be classified as culture negative, culture positive, contaminated, culture result missing, participant died, or participant lost to follow-up (if lost to follow-up prior to that time point).

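### The sample-size section labels 95% CI half-widths (0.101, 0.124) as widths, and the figures are for EBA in logCFU, which is not a planned measurement in this trial

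*Protocol*

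**What the plan says.** Protocol 15.1 sets the size at "15 participants per arm with a total of 75 participants" and gives three supports for it. The first is that this number suffices for population PK and exposure-response modelling; no figures accompany it. The second is that it matches other trials of the type and allows for up to 3 drop-outs per group. The third is numerical and starts from an SD: "Previous Phase IIA (EBA) studies indicate that the between patient standard deviation of logCFU can be approximately 0.2". From that SD the protocol derives standard errors of the group mean EBA and the "corresponding width of 95% confidence intervals are 0.052 and 0.101 respectively for a group size of 15 and 0.063 and 0.124 respectively", where the second pair belongs to a group size of 10.

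SAP 4.3 carries the same paragraph: "expected standard errors of group mean EBA and corresponding width of 95% confidence intervals are 0.052 and 0.101 respectively" for a group size of 15. Both documents then conclude: "This level of precision with a group size of 15 is considered adequate".

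The measurements planned in this trial are different. Under Protocol 9.1.2 the primary efficacy endpoint is change in mycobacterial load "as quantified by time to positivity in BD MGIT 960". In SAP section 10 "the change in liquid culture MGIT time to positivity (TTP) will be modeled and linked to derived PK metrics". Solid (LJ) culture is analysed by status only (SAP 12.2): "Participants will be classified as culture negative, culture positive, contaminated, culture result missing, participant died, or participant lost to follow-up".

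**The concern.** Two things look wrong in the one numerical paragraph behind the sample size.

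First, a 95% interval built from a standard error of 0.052 should run about 0.2 from end to end, not 0.101. The printed figure looks like the plus-or-minus margin under the wrong name. A reader who takes the word literally will believe the interval is half its real length.

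Second, the quantity is a group mean EBA in logCFU, carried over from 14-day-type Phase IIA work. The plan contains no CFU count and no EBA among its endpoints or analyses. The assumption of similar variability therefore applies to a variable for which no measurement is planned, and says nothing about how precisely TTP decline or the exposure-response relationship will be estimated.

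The stake is the credibility of the justification, not the validity of any planned analysis. The adequacy statement follows directly on these figures, and neither document gives a TTP variance, an effect size, a power calculation or a simulation that could stand in for them.

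**Working it through.** **Inputs** (Protocol 15.1, identical in SAP 4.3)
- Between-patient SD of logCFU: 0.2
- Group sizes shown: 15 and 10. The allowance of 3 drop-outs leaves 15 − 3 = 12, which the text does not show.
- Confidence level: 95%. Sidedness is not stated; the two-sided 1.96 reproduces the printed figures.

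**Formulas**
- SE = SD / √n
- Half-width = 1.96 × SE
- Full width = 2 × 1.96 × SE

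**Results**

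| n | SE | Half-width | Full width | Printed as width |
|---|---|---|---|---|
| 15 | 0.2/√15 = 0.0516 | 0.1012 | 0.2024 | 0.101 |
| 12 | 0.2/√12 = 0.0577 | 0.1132 | 0.2263 | not shown |
| 10 | 0.2/√10 = 0.0632 | 0.1240 | 0.2479 | 0.124 |

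The printed SEs (0.052 and 0.063) are reproduced. The printed widths match the half-width column to three decimals. The ratios of printed to full width are 0.101/0.2024 = 0.499 and 0.124/0.2479 = 0.500.

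**Other readings tried**
- t quantiles with n − 1 degrees of freedom: half-widths 0.111 and 0.143, full widths 0.222 and 0.286.
- One-sided 95% bound, 1.645 × SE: 0.085 and 0.104.
- 2 × 1.645 × SE: 0.170 and 0.208.

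None of these gives 0.101 or 0.124. Only 1.96 × SE does.

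**Size of the label error, for illustration only**
- If 0.101 were the full width at n = 15, coverage would be 2Φ(0.0505/0.0516) − 1 = 0.672. If 0.124 were the full width at n = 10, it would be 2Φ(0.062/0.0632) − 1 = 0.673. Both are about 67%, not 95%.
- For those to be full 95% widths at the planned n, the SD would have to be about 0.10: 0.101 × √15 / (2 × 1.96) = 0.0998 and 0.124 × √10 / (2 × 1.96) = 0.1000.
- At SD 0.2, a full 95% width of 0.101 needs (2 × 1.96 × 0.2 / 0.101)² = 60.3 per group, and 0.124 needs 40.0.

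**Is the quantity measured in this trial?**
- Primary efficacy: MGIT TTP by non-linear mixed-effects modelling (Protocol 9.1.2 and 15.4; SAP 5.1.2 and 10).
- LJ solid culture: WK00, WK08, WK12, WK16 and follow-up only, reported as a category (SAP 12.2). With nothing between WK00 and WK08, and no counts planned, an early daily fall in logCFU cannot be estimated.
- Exploratory bacterial load: MBLA and sputum LAM (Protocol 9.2.5).
- LogCFU results appear only in the account of the earlier Phase 2a study (Protocol 6.1.4).

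**The case against.** The strongest reply is that this is a slip of wording with no consequence. Each printed number is a correct calculation of something, and the SE stands beside each interval figure, so an alert reader can see that 0.101 is about twice 0.052 and must be a margin. The size of 15 was not solved from the width, and no analysis, review rule or dose decision uses it. The sponsor may have judged adequacy on the SE or on ±0.101, both of which are right. All of this stands, and it limits the point to a correction of the text. It does not remove the error: neither document defines width as half-width or prints a ± sign, and the figure leads straight into the conclusion on adequacy.

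A second reply is that if EBA is not an endpoint here, mislabelling its interval cannot mislead anyone about this trial. That makes the second half of the point the more important one: the fix must say that these figures do not describe the TTP analysis, and not only relabel them.

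Third, 0.202 and 0.248 treat the SD as known. With an estimated SD, t intervals would be wider: 0.222 at n = 15, 0.286 at n = 10 and 0.254 at n = 12. This is fair. The normal approximation is used above because it is the documents' own convention, and the corrected text should name it.

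Fourth, LJ culture is performed, and its methods are left to a Laboratory Manual that is not among the documents. What the documents support is that no CFU count or EBA is a listed endpoint or planned analysis. The point is put no higher than that.

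**Conclusion.** The concern holds. In both documents the figures called widths are half-widths. Under the stated SD of 0.2 and the two-sided normal approximation that reproduces the text, the full 95% widths are 0.202 (n = 15) and 0.248 (n = 10), twice what is printed. The SD, the group sizes and the SEs are mutually consistent, so this is a labelling error and not a wrong calculation.

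The figures also describe a quantity that the planned measurements cannot yield, and no counterpart is given for TTP. The only number offered for the precision of 15 per arm is thus mislabelled by a factor of two and belongs to a different outcome. The coverage and group-size figures in the working show only how large the label error is; they are not an argument for enrolling more participants. The point should be corrected, and it biases no planned estimate.

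**What to change.** In Protocol 15.1 and SAP 4.3:

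1. Restate the figures as 95% CI half-widths of 0.101 (full width 0.202) for n = 15 and 0.124 (full width 0.248) for n = 10, by normal approximation with the SD taken as 0.2. Optionally add n = 12, the number left after the stated drop-out allowance: half-width 0.113, full width 0.226. If t intervals are preferred, the full widths are 0.222 (n = 15), 0.254 (n = 12) and 0.286 (n = 10).
2. Say plainly that these are EBA figures based on earlier studies and are not the precision of the primary TTP analysis.
3. Tie the conclusion on adequacy to the corrected figures or, better, to the expected precision of the TTP decline or exposure-response estimate. If no such estimate is available, say so.

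The cost is the wording of one paragraph in each document. Protocol 18.7 requires an amendment for any protocol change, with minor administrative ones submitted to the ethics committee for notification as appropriate. Enrolment, data collection and analysis do not change. An added statement of TTP precision would need a short calculation or simulation by the pharmacometrics team.
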